7.2.14.5 MNWS – Minnesota Nicotine Withdrawal Scale

The MNWS will be used at all visits after "quit day" (V4 through V7) to assess nicotine withdrawal symptoms including craving and mood effects. Participants will be asked to assess the following seven symptoms (on a 5-point scale ranging from 0 to 4, where 0 = none, 1 = slight, 2 = mild, 3 = moderate, 4 = severe):

- Desire or craving to smoke
- Anger, irritability, frustration
- Anxiety or nervousness
- Difficulty of concentrating
- Impatience, restlessness
- Hunger
- Depression

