8.5 Post-Quit Sessions (V4-V7)

Sessions scheduled after the quit-smoking date will be conducted at 2 weeks after the quit date and then at 4-week intervals until the end of the 12-week treatment period. The sequence of the following assessments will be at the discretion of the Investigator or designee.

- Document concomitant disease and medication changes
- Physical examination (if indicated)
- Expired air CO breath test
- Vital signs (blood pressure, heart rate, respiratory rate)
- Weight
- Brief review of smoking cessation counseling (if indicated)
- Urine pregnancy test (all females)
- Collection and dispensing of study drugs (collection only at the EOS visit)
- Assess medication compliance
- Verification of proper use of the SMS messaging (refresher training, if needed)
- Questionnaires
 - o FTND
 - o PSS-10
 - MNWS
 - o 6-Item STAI
 - o Adverse Effects Questionnaire
 - Patient Health Questionnaire (PHQ-9)
 - Smoking Status (review with participant and continue daily via SMS survey until End of Study)
 - Medication Compliance (review with participant and continue daily via SMS survey until End of Study)

8.6 6-Month Follow Up

Participants who successfully complete the study and are abstinent at the final visit (V7), will be contacted six months after the quit day utilizing an automated SMS messaging system, to ascertain their current smoking status.

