8.8 SMS Messaging

- 8.8.1 Daily SMS Message (after enrollment, prior to V2) Participants will receive a text with a link to a survey to access the following:
 - How soon after you wake up did you smoke your first cigarette?
 - 1-Within 5 Minutes, 2-6 to 30 Minutes, 3-31 to 60 Minutes, 4-After 60 Minutes
 - How many cigarettes did you smoke today?
 - What was your level of stress today?
 - 1-No Stress, 2-Mild Stress, 3-Moderate Stress, 4-A Lot of Stress, 5-Extreme Stress
 - · How well did you sleep last night?
 - 1-No problems, 2-Mild problems, 3-Moderate problems, 4-A Lot of problems, 5-Extreme problems
 - Did you feel nauseated today?
 1-No nausea, 2-Mild nausea, 3-Moderate nausea, 4-A lot of nausea, 5-Extreme nausea
- 8.8.2 Daily SMS Message (after Visit 2) -- Participants will receive a text with a link to a survey to assess the following:
 - Have you smoked any cigarettes today?
 - If yes, how soon after you wake up did you smoke your first cigarette?
 1-Within 5 Minutes, 2-6 to 30 Minutes, 3-31 to 60 Minutes, 4-After 60 Minutes
 - O How many cigarettes did you smoke today?
 - Did you take your study drugs this morning?
 - Did you take your study drugs this evening?
 - What was your level of stress today?
 - 1-No Stress, 2-Mild Stress, 3-Moderate Stress, 4-A Lot of Stress, 5-Extreme Stress
 - How well did you sleep last night?
 - 1-No problems, 2-Mild problems, 3-Moderate problems, 4-A Lot of problems, 5-Extreme problems
 - Did you feel nauseated today?
 - 1-No nausea, 2-Mild nausea, 3-Moderate nausea, 4-A lot of nausea, 5-Extreme nausea
- 8.8.3 6-Month follow up SMS Message -- Participants will receive a text with a link to a survey to assess the following:
 - Have you smoked a cigarette since your last visit?
 - o If yes, are you still smoking cigarettes right now?

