12.4 Missing Data

Missing data will remain as missing, i.e., no attempt will be made to impute missing values and only observed values will be used in data summarizations and analysis.

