13.1 EFFICACY AND TOLERABILITY

13.1.1 Abstinence Outcomes

Abstinence at each time point will be defined by a self-report of no cigarette smoking (not even a puff) since the prior session, confirmed by an expired air CO reading of less than 5 ppm. The primary

abstinence outcome will be abstinence during weeks 8-11 post-quit date. An intent-to-treat approach will be taken in which any participants lost to follow-up after the point of randomization, or who have relapsed prior to the end of treatment (week 11 post-quit) will be counted as non-abstinent (in accordance with recent guidelines from the FDA). A secondary smoking abstinence outcome will be 7day point abstinence at 6 months post-quit, for participants who have not relapsed prior to the end of treatment. The main goal of the 6-month follow-up is to assess the persistence of therapeutic effects for those who do achieve end-of-treatment abstinence. This information will be helpful in determining the treatment duration in future Phase 3 clinical trials. The main hypothesis to be evaluated in this pilot study is that the incidence of varenicline-associated side effects, specifically nausea, will be diminished by co-administration of hydroxyzine, relative to historical benchmarks (see below). A one-tailed test of abstinence will be conducted, however, comparing the proportion of participants abstinent during weeks 8-11 to the historical benchmark of 45% abstinence, to provide evidence that abstinence is not significantly lower than it would be with varenicline alone. There is no reason to expect that abstinence rate would be reduced by hydroxyzine; if anything, abstinence would be expected to be enhanced by amelioration of varenicline-associated side effects and by potential effects of H1 antagonists to reduce nicotine reward.35

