Appendix 19 – 6-Month Follow Up Survey

* 1. Hello {{ custom.fname }} Did you smoke a cigarette since your last visit?
○ Yes
○ No
2. If yes, are you still smoking cigarettes right now?
○ Yes
○ No

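### The 6-month SMS survey has no 7-day window, so a participant who lapsed and then stopped cannot be scored on the named 7-day abstinence outcome

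*Combined protocol and SAP*

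**What the plan says.** Section 13.1.1 sets the outcome: "A secondary smoking abstinence outcome will be 7day point abstinence at 6 months post-quit", for participants who had not relapsed by the end of treatment. The same section opens with a general definition: "Abstinence at each time point will be defined by a self-report of no cigarette smoking (not even a puff) since the prior session", with an expired-air CO reading below 5 ppm as confirmation.

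Section 8.6 describes the contact. Participants who complete the study and are abstinent at V7 "will be contacted six months after the quit day utilizing an automated SMS messaging system, to ascertain their current smoking status". Section 8.8.3 and Appendix 19 give the survey, which has two Yes/No items. The first is "Have you smoked a cigarette since your last visit" (slightly reworded in the appendix). The second is "If yes, are you still smoking cigarettes right now". No date of last cigarette is asked. The schedule in Section 8.7 marks smoking status at 6 months but no CO test.

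On missing data, Section 12.4 says that "no attempt will be made to impute missing values and only observed values will be used in data summarizations and analysis".

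On the minor matter, Section 2.1.3 gives the Minnesota Nicotine Withdrawal Scale (MNWS) at every laboratory session after enrollment, which by the schedule's column heading means V2 to V7. Section 7.2.14.5 places it after quit day: "V4 through V7) to assess nicotine withdrawal symptoms including craving and mood effects". The V2 and V3 lists (Sections 8.3 and 8.4) omit it, and the schedule marks only V4 to V7. Section 2.3 plans to correlate craving and other withdrawal symptoms, measured by standardized questionnaire in the week before quitting, with end-of-treatment abstinence.

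**The concern.** The instrument and the outcome use different time windows. The survey looks back to V7 and then asks about the present moment, while the outcome concerns the last seven days. The mismatch is harmless for people who never smoked after V7 and for those who are smoking now. It matters for people who smoked at some point and then stopped, the group that separates point abstinence from continuous abstinence.

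Section 13.1.1 gives the follow-up a purpose: to judge how well the effect persists and to inform treatment duration in later trials. If the scoring of this group is settled after the replies are in, in an open-label study, the 6-month rate could reflect that choice. The missing information was never asked for, so the collected data could not supply it later.

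For the MNWS, what is at stake is smaller. Under the schedule, one of several pre-quit predictors has no withdrawal scale behind it.

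**Working it through.** The plan gives no target rate, test or sample-size figure for the 6-month outcome, so there is no stated figure to reproduce. The check sets each possible reply against the outcome and then sizes one ambiguous reply.

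**1. Look-back covered by the first item.** Take 6 months as 26 weeks post-quit (assumption). Section 13.1.1 puts end of treatment at week 11 post-quit: 26 − 11 = 15 weeks = 105 days. Section 8.5 schedules the post-quit visits at "2 weeks after the quit date and then at 4-week intervals until the end of the 12-week treatment period". Counting four visits at that spacing gives weeks 2, 6, 10 and 14, hence 26 − 14 = 12 weeks = 84 days. These two placements of V7 do not agree, but either look-back far exceeds 7 days: 7/105 = 6.7% and 7/84 = 8.3% of it.

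**2. Classification of each reply** (CO confirmation set aside, since none is scheduled)

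| Reply | Named 7-day outcome | General definition (13.1.1) | Current status (8.6) |
|---|---|---|---|
| No | abstinent | abstinent | abstinent |
| Yes, Yes | not abstinent | not abstinent | not abstinent |
| Yes, No | undetermined | not abstinent | abstinent |
| Yes, blank | undetermined | not abstinent | undetermined |

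The second row takes smoking at present to imply smoking within 7 days. In the third row the last cigarette may lie inside or outside the 7 days, and the reply is the same.

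**3. Whether another provision settles it.**
- Daily smoking texts run only through the End of Study (Section 7.2.14.16), so no diary covers the week before the 6-month contact.
- The intent-to-treat rule in Section 13.1.1 concerns loss to follow-up and relapse before the end of treatment. A person who replies Yes, No was abstinent at V7 and has replied, so is neither.
- Section 12.4 concerns missing values, and this reply is observed.

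**4. Effect of one ambiguous reply.** Inputs are the 45% abstinence benchmark (Section 13.1.1), used as a stand-in for abstinence at V7, and N = 25 or 50 (Section 13.1.2). Everyone contacted is assumed to reply.
- Contacted: 0.45 × 25 = 11.25; 0.45 × 50 = 22.5.
- Shift among those contacted: 100/11.25 = 8.9 points; 100/22.5 = 4.4 points.
- Shift among all enrolled: 100/25 = 4 points; 100/50 = 2 points.
- If 35% to 55% were abstinent at V7 (assumed range), 8.75 to 13.75 people are contacted at N=25, giving 11.4 to 7.3 points each. At N=50 it is 17.5 to 27.5 people, giving 5.7 to 3.6 points each.

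The gap between the two readings is the number of Yes, No replies times these values. It is zero if there are none.

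**5. MNWS before the quit date.** There are two administrations (V2, V3) under Section 2.1.3 and none under Section 7.2.14.5, the visit lists and the schedule.

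**The case against.** A reader might infer that the documents contain no rule at all for a Yes, No reply. That goes too far. The general definition in Section 13.1.1 is written for every time point and would count any Yes as non-abstinent. Section 8.6 describes the contact as finding out present status, which would count Yes, No as abstinent. The fair criticism is that these readings compete, nothing says which governs, and neither is a 7-day measure. The first amounts to continuous abstinence since V7.

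It can also be said that if Yes, Yes is accepted as smoking within 7 days, Yes, No should be accepted as 7-day abstinence. The two are not symmetrical. Someone who says they are still smoking has very probably smoked within a week, but someone not smoking at the moment may well have smoked three days ago.

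The objection on weight largely stands. The outcome is secondary, and no benchmark or test is attached to it. The first item speaks directly to whether abstinence persisted. The figures above are per reply, with an unknown count.

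On the MNWS, Section 2.3 does not name that scale. Other measures exist before quitting: a craving item in WI-PREPARE, mCEQ items on relief from smoking, the present-tense STAI, and daily texts rating stress and sleep over 24 hours. A reader might infer that the predictor cannot be assessed at all. The documents do not support that: it would rest on partial proxies, none of which is a withdrawal scale.

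**Conclusion.** The point holds as a mismatch between a named secondary outcome and the only instrument scheduled to measure it. It is confined to people who report smoking since V7 and do not report smoking at present; other replies can be classified. CO confirmation, which the general definition requires, is not scheduled at 6 months.

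The per-reply shift of about 9 or 4.4 points among those contacted rests on the benchmark holding at V7 and on full response. The total effect cannot be stated. It would be wrong to infer that the 6-month rate will be biased, or that the follow-up is uninformative; the documents show only that the rate could turn on an unstated choice. The nausea decision rule and the week 8–11 abstinence outcome do not use these data.

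The change should be made because it is cheap and the information cannot be recovered afterwards. The MNWS contradiction is real but minor.

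**What to change.** Add to Section 8.8.3 and Appendix 19 the item 'Have you smoked a cigarette, even a puff, in the past 7 days?', put to everyone contacted whatever they answer to the existing items. State in Section 13.1.1 that the 6-month outcome is scored from this item and is self-reported without CO confirmation. The existing first item can stay as a descriptive measure of continuous abstinence since V7.

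Reconcile the MNWS passages in one of two ways. Either add the existing form at V2 and V3 in Section 7.2.14.5, Sections 8.3 and 8.4 and the schedule, or correct Section 2.1.3 and name in Section 2.3 the pre-quit measures that serve as the withdrawal predictor.

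The cost is one survey item for roughly 11 to 23 people, plus either a short form at two existing visits or a text correction. It needs a minor amendment with IRB approval and no new visits. To help, the new item must be in place before the 6-month contacts begin.

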9 RISK / BENEFIT INFORMATION

9.1 POTENTIAL BENEFITS

The participants will be encouraged to quit smoking, which would significantly reduce their risk of smoking-related diseases.

9.2 IMPORTANCE OF KNOWLEDGE TO BE GAINED

By conducting the proposed research, we may develop a new approach to smoking cessation treatment that promises to help a significantly larger proportion of smokers to quit successfully. This would have a major positive impact on public health.

9.3 POTENTIAL RISKS

Continuing to smoke carries significant health risks; if participants are successful at maintaining abstinence (and possibly quit), the participants in the studies will realize a significant improvement in their health and a decrease in their risk of morbidity and mortality associated with smoking combustible cigarettes.

9.3.1 Hydroxyzine

Hydroxyzine is a first-generation antihistamine which has FDA-approval as an antiemetic, anxiolytic, and sedative medication. Even with its effective sedative, hypnotic, and anxiolytic effects, hydroxyzine does not demonstrate any of the abuse, dependence, addiction or toxicity potential associated with medications within the same therapeutic range (such as benzodiazepines or nonbenzodiazepine hypnotics). A common adverse event for hydroxyzine (occurring 10% or more) is drowsiness. All other adverse events occurred less than 10% or were of unknown incidence. This includes dry mouth, cough, unusual tiredness, and irregular or slow heart rate. Studies of hydroxyzine have shown a lack of organ toxicity and absence of dependence. Case reports of QT prolongation and Torsade de Pointes have been reported during post-marketing analysis. These reports were noted to occur in patients with other risk factors for QT prolongation.

9.3.2 Varenicline

Varenicline is one of the most widely used prescription medications for smoking cessation. Common adverse events associated with varenicline include nausea, insomnia, abnormal dreams, headaches, and nasopharyngitis. ¹⁹ The most common adverse reaction reported is nausea, with 30-40% of participants in randomized control trials reporting mild to moderate levels of nausea. ³³ Discontinuation/drop-out rates of nearly 10% have been noted during clinical trials due to these adverse effects. ³⁴ In addition to the potential drug-specific side effects noted, any medication may trigger a serious allergic reaction and may cause shock, seizures (convulsions, epilepsy, "fits"), loss of consciousness, tingling, swelling of the face, lips, tongue, throat and/or vocal cords, difficulty breathing, asthma, wheezing, rash, hives, itching, and possibly death.

9.3.3 Nicotine Withdrawal

Participants may experience nicotine withdrawal symptoms, including craving, difficulty concentrating, nausea, insomnia, headache, mood disturbance and increased appetite/weight gain.

9.3.4 Blood Draw

The risks associated with venipuncture are minimal and include momentary discomfort and/or bruising. Infection, excess bleeding, clotting, and fainting are also possible, although unlikely.

9.4 PROTECTION AGAINST RISKS

Participants will be screened medically and monitored throughout the study. Participants will be instructed to report any side effects to study staff, who will communicate these reports immediately to the medical staff. The most appropriate course of action will be determined, which may include options for dose reduction or termination of treatment. Participants whose treatment is terminated will be encouraged to remain in the study for assessment of outcomes and to receive continuing social support for quitting smoking. Participants will, however, be reminded that they have the option to withdraw from the study at any time. Participants will also be given the 24-hour emergency contact number in the event that side effects or adverse events occur between sessions.

9.4.1 Blood Pressure Monitoring

After study enrollment, if blood pressure during laboratory visits is above 160/100, then the following actions will be taken to enhance participant safety:

- If BP >210/120 with symptoms of malignant hypertension, all experimental interventions will be stopped immediately, and the participant will be referred to appropriate medical treatment. Participation may resume, with continued monitoring, if BP is no greater than 150/100.
- If BP > 160/100 for 2 consecutive sessions, the Center will request that the participant have their BP checked weekly by their PCP, local pharmacy, or home machine and call us with results. Participants will also be encouraged to see their PCP regarding evaluation, treatment, and further monitoring.

10 QUALITY CONTROL AND QUALITY ASSURANCE

10.1 Training of Staff

The Investigator or designee will ensure that appropriate training relevant to the study is provided to all staff involved in the study, and that any new information relevant to the performance of this study is forwarded in a timely manner to the staff.

10.2 AUDITS AND INSPECTIONS

Good Clinical Practice regulations require independent inspections of clinical program activities. Such inspections may be performed at any time before, during, and after the study.

Authorized representatives of the Sponsor, regulatory agencies and/or an IRB may perform audits or inspections, including source data verification. The purpose of an audit or inspection is to systematically and independently examine all study-related activities and documents to determine whether these activities were conducted, and data were recorded, analyzed and accurately reported, according to the protocol, ICH/GCP guidelines and any applicable regulatory requirements. The Investigator or designee will contact the Sponsor immediately if contacted by a regulatory agency about an inspection at their site.

The Investigator and study staff are responsible for maintaining a comprehensive and accurate filing system of all study-related documentation that will be suitable for inspection at any time by the Sponsor, its authorized representative, and other regulatory agencies.

11 Reporting of Adverse Events

11.1 DEFINITIONS

11.1.1 Adverse Event

An Adverse Event (AE) is defined as any untoward medical occurrence that may present during participation in the study and which may or may not have a causal relationship with study procedures and/or products tested in this study. An adverse event (AE) can therefore be any unfavorable and unintended sign (including an abnormal laboratory finding, for example), symptom, or disease temporally associated with the use of a medicinal product, whether or not considered related to the study procedures and/or products.

Any increase in the severity and/or the frequency of a concomitant disease is considered an AE.

11.1.2 Serious Adverse Event

A Serious Adverse Event is any adverse event that:

- results in death;
- is life-threatening;
- results in inpatient hospitalization or prolongation of existing hospitalization;
- results in persistent or significant disability / incapacity;
- results in a congenital anomaly / birth defect;
- requires immediate medical or surgical intervention.

Important medical events that may not result in death, be life threatening, or require hospitalization may be considered an SAE, when, based on appropriate medical judgment, the event may jeopardize the participant, or the participant may require medical or surgical intervention to prevent one of the outcomes listed in the above definitions.

The term "life-threatening" in the definition of "serious" refers to an event in which the participant was at risk of death at the time of the event; it does not refer to an event, which hypothetically might have caused death if it were more severe.

Any pre-planned hospitalizations that are known at the time of signing the ICF will not be recorded as an SAE; however, they will be recorded as AE only. Any AE that occurs during this pre-planned hospitalization will be considered according to the above definitions.

11.2 COLLECTION OF SAFETY EVENTS FROM PARTICIPANTS

Information recorded when collecting AEs will include: thorough description of the AE, seriousness assessment, start and stop dates (if known), circumstances leading up to the event, clinical elements such as clinical course, specific vital signs and test results that may explain the pathophysiology of the event, as well as alternative explanations to its occurrence, the action taken with the investigation

product/procedures due to the AE, the participant's disposition in the study after the occurrence of the AE and the final outcome of the AE (if known).

Any exacerbation/worsening or increased frequency of an AE or pre-existing condition shall be evaluated and recorded.

AEs should be collected using questionnaires and face-to-face interviews with the participant. The Adverse Effects Form is a targeted checklist-based questionnaire with items selected to detect common side effects from product use. This questionnaire also contains an open-ended section for participants to record any additional effects.

Whenever a medically meaningful diagnosis is available to comprise a set of reported signs and/or symptoms, it should be preferentially provided as the AE or SAE term, rather than the individual signs and/or symptoms. Otherwise, each one of those signs and/or symptoms should be reported separately as event terms.

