6 VARENICLINE

6.1 Description of Varenicline

Varenicline is one of two FDA-approved non-nicotine medications prescribed as a smoking cessation aid. It is a partial agonist of the $\alpha4\beta2$ nACHR. Due to its relatively long half-life, compared to nicotine, varenicline also acts as an antagonist, blocking occupied receptors from additional stimulation from nicotine. Recognized as one of the most effective monotherapy treatments for tobacco dependence, the medication increases the odds of quitting smoking by nearly fourfold compared with placebo. Hays et al. found varenicline to be generally safe and well tolerated as a smoking cessation aid. Common adverse events associated with varenicline (occurring 10% or more) include nausea, insomnia, abnormal dreams, headaches, and nasopharyngitis. ¹⁹ Nausea, the most common side effect of varenicline, has been reported as high as 30%. Abnormal dreams and insomnia have been reported by over 10% of users. $^{27-29}$

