6.3 Dose Adjustment Procedures

Dose adjustments for varenicline will be performed by licensed medical providers based on adverse effects reported by participants (e.g. insomnia, abnormal dreams, mood disturbances, anxiety...decrease dose to 0.5 mg twice a day for moderate to severe side effects). Participants will be contacted with a follow-up call by Research Medical Staff within 72 hours of any dose adjustment.

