Appendix 4 – Minnesota Nicotine Withdrawal Scale Revised (MNSW-R)

MINNESOTA NICOTINE WITHDRAWAL SCALE REVISED (MNWS-R)

INSTRUCTIONS: Please rate yourself based on the last 24 hours.

	None	Slight	Mild	Moderate	Severe
1. Angry, irritable, frustrated	0	0	0	0	0
2. Anxious, nervous	0	0	0	0	0
3. Depressed mood, sad	0	0	0	0	0
4. Desire or craving to smoke	0	0	0	0	0
5. Difficulty concentrating	0	0	0	0	0
6. Increased appetite, hungry, weight gain	0	0	0	0	0
7. Insomnia, sleep problems, awakening at night	0	0	0	0	0
8. Restless	•	0	0	0	0
9. Impatient	0	0	0	0	0
10. Constipation	0	0	0	0	0
11. Dizziness	•	0	0	0	0
12. Coughing	0	0	0	0	0
13. Dreaming or nightmares	0	0	•	0	0
14. Nausea	0	0	0	0	0
15. Sore throat	0	0	0	0	0

ı

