Appendix 13 – Adverse Effects Form

ADVERSE EFFECTS FORM

Are you currently experiencing, or have you experienced any of the following since your previous visit?											
INTENSITY RATINGS: Mild – Easily tolerated and did not interfere with daily activity Moderate – Interfered with daily activity, but you were still able to function Severe – Incapacitated and required medical intervention					FREQUENCY RATINGS: Rarely – Just once Occasionally – A few times Frequent – Several times / most of the time Very Frequent – Everyday / constantly						
Adverse Effect	N/A	Mild	Moderate	Severe	Rarely	Occasionally	Frequent	Very Frequent			
Headache											
Drowsiness (feel sleepy)				0							
Fatigue	D										
Nausea											
Vomiting											
Unusual heart rate											

Are you experiencing (or have you experienced) any other effects not listed above? If yes, please list one item on each row below and rate accordingly.										
INTENSITY RATINGS: Mild — Easily tolerated and did not interfere with daily activity Moderate — Interfered with daily activity, but you were still able to function Severe — Incapacitated and required medical intervention				FREQUENCY RATINGS: Rarely – Just once Occasionally – A few times Frequent – Several times / most of the time Very Frequent – Everyday / constantly						
Adverse Effect	N/A	Mild	Moderate	Severe	Rarely	Occasionally	Frequent	Very Frequent		

MD/ PA Signature	Date	

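### The Adverse Effects Form has no prompted row for abnormal dreams, a common varenicline effect, so under the visit schedule no item naming dreams is asked before V4, about treatment day 21.

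*Combined protocol and SAP*

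**What the plan says.** On the purpose of the form, section 11.2 states: "The Adverse Effects Form is a targeted checklist-based questionnaire with items selected to detect common side effects from product use". Appendix 13 opens with "Are you currently experiencing, or have you experienced any of the following since your previous visit" and prints six rows: headache, drowsiness, fatigue, nausea, vomiting and unusual heart rate. Blank rows follow under "Are you experiencing (or have you experienced) any other effects not listed above", with the same intensity and frequency ratings.

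On dreams, section 6.1 says "Abnormal dreams and insomnia have been reported by over 10% of users". Section 6.3 gives as its example of a dose adjustment "insomnia, abnormal dreams, mood disturbances, anxiety...decrease dose to 0.5 mg twice a day for moderate to severe side effects".

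One reviewed instrument names dreams: the 15-item withdrawal scale (MNWS-R) in Appendix 4. Its item 13 is "Dreaming or nightmares" and its instruction is "Please rate yourself based on the last 24 hours". Sections 7.2.14.5 and 8.7 place the scale at V4 to V7, and the visit lists in 8.3 and 8.4 (V2 and V3) omit it.

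Two passages do not fit that picture. Section 2.1.3 has the scale given at every laboratory session after enrollment. Section 7.2.14.5 describes a shorter instrument ("Participants will be asked to assess the following seven symptoms"), and its list contains no dream item.

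**The concern.** A targeted checklist exists so that a common, expected effect does not depend on the participant thinking to mention it. The protocol itself names abnormal dreams as common with varenicline, and section 1.1 makes easing sleep disturbance one of the reasons for adding hydroxyzine. The form nonetheless gives dreams no row.

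The stake is ascertainment. Section 13.1.2 will tabulate side effects that are new or aggravated after treatment starts. For dreams there would be no prompted pre-drug rating against which to judge aggravation, and counts up to V4 would reflect who volunteers them. A low early count could then mean that hydroxyzine helps or that nobody was asked, and the data could not tell these apart.

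Insomnia, mood and anxiety are not part of this point. The daily SMS survey, PHQ-9 and STAI already ask about them.

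**Working it through.** The plan gives no figure to reproduce here. The check is a reading of the instruments followed by visit-day arithmetic.

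**Where dreams are named**

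| Instrument | Names dreams? | When asked |
|---|---|---|
| Adverse Effects Form (Appendix 13) | No: 0 of 6 printed rows | V2-V7 |
| Daily SMS (8.8, Appendices 14 and 16) | No: general sleep item | Daily from the observation period |
| PHQ-9 item 3 (Appendix 3) | No: sleep trouble only | V1-V7 |
| Medical History and Review of Systems (Appendices 10 and 11) | No: insomnia, sleep trouble | V1 |
| Withdrawal scale, item 13 (Appendix 4) | Yes, 24-hour recall | V4-V7 under 7.2.14.5 and 8.7 |

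Under 8.7, a named dream item is asked at 4 of the 6 visits V2-V7, and at 0 of the first 2.

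**When the first one falls** (day 0 = first dose)

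- V3 = day 6 (8.4). Quit date = day 7 (8.3).
- V4 is two weeks after the quit date (8.5): 7 + 14 = day 21.
- The four-day window (4.8.2), applied to V4 alone, gives 21 − 4 = 17 to 21 + 4 = 25.
- If a shift in V3 is assumed to move the quit date as well, the quit date is day 3 to 11 and V4 is nominally day 17 to 25. V4's own window then widens this to day 13 to 29.

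**What the V4 item covers**

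- Full dose starts on day 7. Days 7 to 20 are the first 14 full-dose days.
- A 24-hour recall at day 21 reaches only day 20, so 14 − 1 = 13 of those 14 days fall outside it.
- A row on Appendix 13 asks about the time since the previous visit. At V4 that is 21 − 6 = 15 days.
- With such a row, the first on-treatment prompt is V3, day 6, which is 21 − 6 = 15 days earlier than now.

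No day counts are used after V4. Literal four-week intervals from day 21 give days 49, 77 and 105, and the last is past a 12-week (84-day) course.

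**How many participants the effect might concern** (assuming the 10% floor in 6.1 holds here)

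- Expected cases: 0.10 × 25 = 2.5 and 0.10 × 50 = 5.
- Chance of at least one case: 1 − 0.9^25 = 0.928 and 1 − 0.9^50 = 0.995.

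These are chances that the effect occurs, not that it is missed. The documents give no basis for estimating how many cases would go unreported.

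**Other readings of the text**

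- If 2.1.3 governs, item 13 is also asked at V2 and V3, making 6 of 6 visits, still with 24-hour recall.
- If the seven-symptom version in 7.2.14.5 is used, dreams are named at 0 of 6 visits.

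**The case against.** The strongest reply is that dreams are solicited, just not by name. At every visit from V2 the form asks about any other effect and has it graded on the same scales. Section 11.2 adds face-to-face interviews, 9.4 tells participants to report any side effect and gives a 24-hour number, and a daily sleep rating begins before the first dose. All of this stands, and the point is limited to prompted collection. An open question is less sensitive than a named row, and the sleep rating cannot separate dreams from other poor sleep.

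Second, the timing claim follows one side of conflicting text. That is true, and 2.1.3 would supply a named item before drug. The schedule, 7.2.14.5 and the visit lists all say V4-V7, however. Under every reading Appendix 13 lacks a row giving a graded rating since the last visit.

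Third, 11.2 does not promise a row for every effect at 10% or more; nasopharyngitis has none either. Fair: this is a design choice, not a contradiction. Dreams differ in being tied to the study's sleep aim and to dose reduction.

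Fourth, nothing confirmatory depends on the count. Side effects are tabulated descriptively, and hypothesis tests are reserved for withdrawal due to side effects and adherence. That also stands, and it limits the severity.

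Finally, the participant instruction sheets (Appendices 17 and 18) are not in the review copy. Any advice there on reporting dreams could narrow the gap.

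**Conclusion.** The concern holds, as a cheap improvement to consider. None of the six prompted rows names an effect that the protocol calls common. Under the schedule in 8.7, the first item naming dreams comes at about day 21 and looks back one day. The consequence is a dream count without a prompted baseline, dependent on volunteered reports for roughly the first three weeks of treatment. The number of cases missed cannot be estimated from the documents.

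The conclusion assumes that 8.7 governs the timing of the withdrawal scale and that the Appendix 4 version is the one used. The missing row itself does not depend on either assumption. A route to dose reduction already exists in 6.3 and 9.4, so no safety path is missing, and the nausea stopping rule and its error rates are untouched.

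**What to change.** Add one prompted row to Appendix 13, abnormal dreams or nightmares, with the existing intensity and frequency ratings, from V2 (before the first dose) through V7. This gives a pre-drug rating and prompts at 6 of 6 visits. It moves the first on-treatment prompt from about day 21 to about day 6 and extends the V4 look-back from 1 day to about 15. An insomnia row is optional, if a grade on the 11.3.1 definitions is wanted. Section 6.3 needs no change.

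The cost is 1 row × 6 visits = 6 entries per participant on a form already in use, plus IRB approval of the changed appendix under 14.1. Prompting will slightly raise the reported count of dreams, so tolerability may look a little less favourable. At V4-V7 dreams would be rated on both the form and the withdrawal scale; the report should say which one feeds the treatment-emergent table. The row does not settle the timing and version of the withdrawal scale, so 2.1.3 and 7.2.14.5 should be reconciled with 8.7 and Appendix 4 in the same amendment.
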